	
Safety: Major adverse cardiac events, which were defined as a non-weighted composite score of: death, stroke, worsening heart failure (+1 NYHA Class), hospitalization for heart failure, and mitral valve re-intervention within 12 months after surgery; and incidence of protocol-defined serious adverse events (especially thromboembolic and hemorrhagic events) within 12 months after surgery.

Follow-up Schedule	
Pre-discharge, and at 30 days, 3, 6, and 12 months after surgery.

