4. OBJECTIVES

Primary objective

The primary objective is to assess the efficacy and safety of the new procedure (left atrial geometric volume reduction, pulmonary veins island isolation and left appendage base closure) for treating long standing persistent AF elimination. Efficacy will be evaluated by freedom from AF within 6 months and 12 months after surgery. Safety will be assessed by a composite of early adverse outcomes (within 30 days post-procedure or hospital discharge, whichever is later), including death, stroke, serious cardiac events (heart failure, myocardial infarction), cardiac re-hospitalizations, transient ischemic attack, pulmonary embolism, peripheral embolism, coronary artery injury, anatomical excessive bleeding, deep sternal wound infection/mediastinitis, damage to specialized conduction system requiring permanent pacemaker, and superior vena cava stenosis. We hypothesize that the new procedure will reduce the risk of AF post-MVS reoccurrence and lower the incidence of adverse outcomes, as compared to that was historically reported in patients undergoing MVS concomitantly with COX MAZE IV.

Secondary objectives

- (a) To assess the incidence of major adverse cardiac events and protocol-defined and serious adverse events (especially thromboembolic and hemorrhagic events) within 12 months after surgery, which is hypothesized to be lower than MVS concomitantly with COX MAZE IV.
- (b) To assess the intra-operation cardiopulmonary bypass time(CPB), which if prolonged could increase risk of poor prognosis within 30 days post-procedure or hospital discharge. CPB time is hypothesized to be shorter than that historically reported in COX MAZE IV procedure.
- (c) To assess the changes of size and shape of left atrium. The post-surgical shape and size of left atrium is hypothesized to be closer to normal status.
- (d) To assess the function of left atrium. The incidence of peak late trans-mitral flow velocity (A) at 12 months post-surgery is supposed to be high.

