8. ENDPOINTS

Primary Endpoints

Efficacy

Freedom from AF in patients with longstanding persistent AF undergoing MVS at 6 months and 12 months. AF will be measured by 7 days continuous Holter monitoring at 6 months and 12 months post-surgery; and freedom of AF will be defined by absence of AF lasting > 30 seconds at 12 months.

Patients will be considered as treatment failures (not free of AF) if: 1) they die prior to the 12-month assessment; 2) or they are determined by an independent adjudicator to be too ill to undergo AF assessment; 3) or they require additional ablation therapy for AF (including surgical ablation or percutaneous catheter ablation) subsequent to the index procedure.

Safety

(a)Cardiopulmonary bypass time, which if prolonged could increase risk of poor prognosis within 30 days post-procedure or hospital discharge;

(b)The adverse events within 30 days after surgery, including: death, stroke, serious cardiac events (heart failure, myocardial infarction), cardiac re-hospitalizations, transient ischemic attack, pulmonary embolism, peripheral embolism, coronary artery injury, anatomical excessive bleeding, deep sternal wound infection/mediastinitis, damage to specialized conduction system requiring permanent pacemaker, and superior vena cava stenosis.

Secondary Endpoints

Efficacy

(a)The changes of size and shape of left atrium, which will be measured by comparing the anteroposterior, transversal, and superoinferior diameters of left atrium between 3 time points (i.e., before surgery, 6 months and 12 months post-surgery) by using transthoracic echocardiography.

(b)The peak late trans-mitral flow velocity (A) at 6 months and 12 months post-surgery, which will be measured by transthoracic echocardiography.

Safety

(a)MACEs within 12 months after surgery: defined as a non-weighted composite score

of: death, stroke, worsening heart failure (+1 NYHA Class), CHF hospitalization, and mitral valve [MV] re-intervention.

(b) Protocol-defined and serious cerebrovascular adverse events (especially thromboembolic and hemorrhagic events) within 12 months after surgery.

(c) All-cause mortality at 12 months after surgery.

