peripheral embolism, coronary artery injury, anatomical excessive bleeding, deep sternal wound infection/mediastinitis, damage to specialized conduction system requiring permanent pacemaker, and superior vena cava stenosis, within 30 days post-procedure or hospital discharge (whichever is later). The rate of these safety endpoints will be calculated within 30 days after surgery.

Secondary Analyses

Efficacy

(a) The size and shape of left atrium. The anteroposterior, transversal, and superoinferior diameters, as well as their ratios, of left atrium between two time points (i.e., before surgery and 12 months post-surgery), will be measured by transthoracic echocardiography. The absolute change and reduction rate of each diameter will be analyzed, and the post-surgery size and shape will be compared with Chinese standards.

(b) Left ventricular ejection fraction and peak late transmitral flow velocity (A) at 12 months post-surgery will be measured by transthoracic echocardiography. These measurements evaluate the function of heart pump.

Safety

(a) Major adverse cardiac events (MACE) defined as a non-weighted composite score of: death, stroke, worsening heart failure (+1 NYHA Class), CHF hospitalization, and mitral valve [MV] re-intervention within 12 months of surgery. The rate of MACE will be calculated and compared with MACE rate historically reported in COX MAZE IV procedure.

(b) Incidence of protocol-defined and serious adverse events (especially thromboembolic and hemorrhagic events) within 12 months of surgery. The rate of SAE will be calculated and compared with MACE rate historically reported in COX MAZE IV procedure.

(c) All-cause mortality at 12 months post-surgery. The Kaplan-Meier curve will be plotted to show the probability of death at a respective time interval and compared with 1-year deaths historically reported in COX MAZE IV procedure.

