13. SPECIFIC ADVERSE EVENT DEFINITIONS

Bleeding

A bleeding event is defined by any one of the following:

- Transfusion of > 2 units RBC within the first 24 hours following surgery
- Death due to hemorrhage
- Re-operation for hemorrhage or tamponade

NOTE: Hemorrhagic stroke is considered a neurological event and not as a separate bleeding event.

Cardiac Arrhythmias

Any documented arrhythmia that results in clinical compromise (e.g., hemodynamic compromise, oliguria, pre-syncope or syncope) that requires hospitalization or requires a physician visit or occurs during a hospital stay.

Cardiac arrhythmias are classified as:

1. Sustained ventricular arrhythmia requiring defibrillation or cardioversion
2. Sustained supraventricular arrhythmia requiring drug treatment or cardioversion
3. Cardiac conduction abnormalities requiring permanent pacemaker

Pericardial Fluid Collection

Accumulation of fluid or clot in the pericardial space that requires surgical intervention or percutaneous catheter drainage. This event will be subdivided into those with clinical signs of tamponade (e.g. increased central venous pressure and decreased cardiac output) and those without signs of tamponade.

Pleural Effusion

Accumulation of fluid or clot in the pleural space documented by chest radiogram or chest CT that requires evacuation with surgical intervention or chest tube placement.

Atrial Rupture

Disruption in the integrity of the left or right atrial wall, documented by direct inspection or diagnostic testing, that necessitates surgical repair.

Valvular Injury

Injury to a cardiac valve (excluding the mitral valve), as evidenced by new regurgitation or stenosis following the treatment intervention. This definition excludes changes to the mitral valve because it will be surgically repaired at the time of the treatment intervention.

Non-infectious Pericarditis

Signs and symptoms of pericardial inflammation, with or without electrocardiographic evidence, requiring pharmacologic anti-inflammatory therapy. This definition excludes infectious pericarditis (see Major Infection infectious pericarditis definition below).

Superior vena cava Stenosis

A \geq 50% decrease in the diameter of the superior vena cava as documented by echocardiography.

Diaphragmatic Paralysis

Phrenic nerve injury as evidenced by new elevation of a hemi-diaphragm on chest radiogram.

Pneumothorax

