Infection localized to any organ system or region other than the mediastinum, pericardium, or endocardium without evidence of systemic involvement (see sepsis definition), ascertained by standard clinical methods and either associated with evidence of bacterial, viral, fungal or protozoal infection, and/or requiring empirical treatment.

Heart Failure

New onset of signs or symptoms of congestive heart failure or worsening of preexisting heart failure by ≥ 1 NYHA class.

Myocardial Infarction

Myocardial infarction (MI) should be classified when there is evidence of myocardial necrosis in a clinical setting consistent with myocardial ischemia.

Under these conditions, any one of the following criteria meets the diagnosis for myocardial infarction⁴:

Myocardial Infarction

Detection of rise and/or fall of cardiac biomarkers (preferably troponin) with at least one value above the 99th percentile of the upper reference limit (URL) together with evidence of myocardial ischemia with at least one of the following:

- Symptoms of ischemia;

- ECG changes indicative of new ischemia (new ST-T changes or new left bundle branch block [LBBB]);
- Development of pathological Q waves in the ECG;
- Imaging evidence of new loss of viable myocardium or new regional wall motion abnormality.

Peri-CABG Myocardial Infarction

For CABG in patients with normal baseline troponin values, elevations of cardiac biomarkers above the 99th percentile URL are indicative of peri-procedural myocardial necrosis. By convention, increases in biomarkers $> 5 \times$ 99th percentile URL plus either new pathological Q waves or new LBBB, or angiographically documented new graft of native coronary artery occlusion, or imaging evidence of new loss of viable myocardium have been designated as defining CABG-related MI.

Peri-Percutaneous Intervention (PCI) Myocardial Infarction

For PCI in patients with normal baseline troponin values, elevations of cardiac biomarkers above the 99th percentile URL are indicative of peri-procedural myocardial necrosis. By convention, increases in biomarkers $> 3 \times$ 99th percentile URL have been designated as defining PCI-related MI. A subtype related to a documented stent thrombosis is recognized.

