Sudden unexpected cardiac death, involving cardiac arrest, often with symptoms suggestive of myocardial ischemia, and accompanied by presumed new ST elevation or new LBBB, and/or evidence of fresh thrombus by coronary angiography and/or autopsy, with death occurring before blood samples obtained, or at a time before the expected appearance of cardiac biomarkers in blood will be classified as a mortality due to MI.

Neurologic Dysfunction

Any new, temporary or permanent, focal or global neurological deficit ascertained by a standard neurological examination (administered by a neurologist or other qualified physician and documented with appropriate diagnostic tests and consultation note). The examining physician will distinguish between a transient ischemic attack (TIA), which is fully reversible within 24 hours (and without evidence of infarction), and a stroke, which lasts longer than 24 hours (or less than 24 hours if there is evidence of infarction). The Modified Rankin Scale and the NIH Stroke Scale (NIHSS) must be administered at time of event (within 72 hours following the event) and 90 days following the event

to document the presence and severity of neurological deficits. The Modified Rankin Scale and NIHSS can be found in Appendix III.

Each neurological event must be subcategorized as: Transient Ischemic Attack

Defined as an acute event that resolves completely within 24 hours with no imaging evidence of infarction.

Ischemic or Hemorrhagic Stroke (Cerebrovascular Accident)

Defined as an event that persists beyond 24 hours or less than 24 hours associated with infarction on an imaging study. Hemorrhagic conversion of an ischemic stroke should be classified as ischemic.

Toxic Metabolic Encephalopathy

Defined as a disorder of the brain function that arises from abnormal systemic metabolism or exogenous substances, altering awareness and/or consciousness, in which there is a non-focal neurological examination and a negative brain image.

Other Neurologic Dysfunction

Renal Events

Two categories of renal events will be identified:

- Renal Dysfunction: Abnormal kidney function defined by $> 100\%$ rise in serum creatinine (Cr) from baseline, and $Cr > 2.0$
- Renal Failure: New requirement for hemodialysis related to renal dysfunction. This definition excludes aquapheresis for volume removal alone.

Respiratory Failure

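### Secondary Safety (b) sets the 12-month SAE rate against a historical Cox-Maze IV MACE rate, so the SAE part of secondary objective (a) has no like-for-like comparator

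*Combined protocol and SAP*

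**What the plan says.** Secondary objective (a) in Section 4 names two outcomes, MACE and protocol-defined and serious adverse events, and puts one hypothesis on both: "especially thromboembolic and hemorrhagic events) within 12 months after surgery, which is hypothesized to be lower than MVS concomitantly with COX MAZE IV".

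Section 12, Secondary Analyses, Safety, then takes the outcomes one at a time:

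- Safety (a) defines MACE as "death, stroke, worsening heart failure (+1 NYHA Class), CHF hospitalization, and mitral valve [MV] re-intervention within 12 months of surgery" and compares it with the MACE rate reported for Cox-Maze IV.
- Safety (b) takes the adverse events and says: "The rate of SAE will be calculated and compared with MACE rate historically reported in COX MAZE IV procedure".
- Safety (c) compares one-year deaths with one-year deaths.

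The adverse-event endpoint is not worded the same way throughout. Section 2 has "incidence of protocol-defined serious adverse events (especially thromboembolic and hemorrhagic events) within 12 months after surgery". Section 8 has "Protocol-defined and serious cerebrovascular adverse events (especially thromboembolic and hemorrhagic events) within 12 months after surgery". Sections 4 and 12 have *protocol-defined and serious*, without the word *cerebrovascular*.

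For Safety (b) the document gives no historical rate, source, event definition, test or margin.

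**The concern.** A historical comparison can only be read if numerator and benchmark count the same kind of event over the same period. Safety (b) counts one set of events and benchmarks it against another. A finding that the SAE rate is lower or higher than the historical MACE rate would mix any effect of the operation with the difference between the two definitions.

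What is at stake is the SAE half of secondary objective (a), for a new operation studied without a concurrent control. The MACE half has its own matched comparison in Safety (a) and is not touched.

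**Working it through.** The plan states no figure for Safety (b), so there is none to reproduce. The check sets definitions side by side.

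**Step 1. What each event set contains.** MACE is taken from Section 12, Safety (a), and the adverse-event categories from Section 13. A *no* means that the event does not count unless it also leads to a MACE component such as death.

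| Event | In MACE? | Category in Section 13 |
|---|---|---|
| Death | yes | Other (fatal events) |
| Ischemic or hemorrhagic stroke | yes | Neurologic Dysfunction |
| Heart failure worse by one NYHA class | yes | Heart Failure |
| Admission for heart failure | yes | Heart Failure, or Other |
| Mitral re-intervention | yes | Other, if it needs hospitalization (Valvular Injury excludes the mitral valve) |
| TIA | no | Neurologic Dysfunction |
| Non-fatal arterial embolism outside the CNS | no | Arterial Non-CNS Thromboembolism |
| Non-fatal venous thromboembolism | no | Venous Thromboembolic Event |
| Non-fatal bleeding: early transfusion or re-operation | no | Bleeding |
| Non-fatal pericardial or pleural clot needing drainage | no | Pericardial Fluid Collection; Pleural Effusion |
| Other serious non-fatal bleeding | no | Other |

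Of the thromboembolic and hemorrhagic events that the endpoint singles out, MACE sees strokes and deaths and little else. Hemorrhagic stroke reaches MACE as a stroke; in Section 13, "Hemorrhagic stroke is considered a neurological event and not as a separate bleeding event".

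**Step 2. Comparator by analysis.** Safety (a) is MACE against MACE. Safety (c) is death against death. Safety (b) is SAE against MACE. Only (b) is mismatched, and no section names a historical SAE, thromboembolic or hemorrhagic rate.

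**Step 3. Can the direction be derived?** It depends on which scope applies.

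- *Protocol-defined and serious*, read as events in either class (Sections 4 and 12). By the table, Section 13 covers every MACE component. At patient level the trial's SAE rate cannot then be below the trial's own MACE rate. But the planned benchmark is a historical MACE rate, in other patients and under an unknown definition, so no order between those two rates follows.
- *Protocol-defined serious*, read as meeting both conditions (Section 2). Section 13 defines heart failure as "New onset of signs or symptoms of congestive heart failure or worsening of preexisting heart failure by" one NYHA class or more. A one-class worsening that is not judged serious counts as MACE but not as SAE. A serious TIA does the reverse. Neither set contains the other.
- *Serious cerebrovascular* (Section 8). Heart failure, mitral re-intervention and deaths without a cerebrovascular cause drop out, while TIA stays in. Again the sets are not nested. The adjective could also be read as limiting only the serious events.

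The direction cannot be settled from the documents.

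**Step 4. Can the size be derived?** Only by assuming every rate, and a test that the plan does not state. As an illustration, take n = 120 and an exact one-sided binomial test at 0.025, calling the rate lower if X ≤ c, where c is the largest k with P(X ≤ k | benchmark rate) ≤ 0.025.

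- Assumed MACE benchmark 20%, so c = 15. Assumed SAE rate 10% both historically and in the trial, so there is no benefit. P(X ≤ 15 | 0.10) = 86%. With a 15% benchmark, c = 10 and the probability is 34%.
- Assumed MACE benchmark 20%. Assumed SAE rate 30% historically and 20% in the trial, so there is a real benefit. P(X ≤ 15 | 0.20) = 2.2%. Against a matched 30% benchmark, c = 25 and the probability is 64%.

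The assumed inputs produce the error in either direction. These figures show why no size can be given; they do not estimate one.

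**The case against.** The strongest reply is that this is a slip with a recoverable intent. Safety (a) and (b) end in the same words about the historical MACE rate, and objective (a) implies that each outcome is compared with its counterpart. The endpoint is secondary, with no test or margin, so no formal decision turns on it. Section 11 also requires the Clinical Events Committee to hold consistent definitions for each type of event.

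Most of this stands and limits the severity. It does not remove the point. The sentence is current text, and nothing elsewhere overrides it. Correcting the one term would still leave the event set open, because Sections 2, 8 and 4/12 word it differently. Consistent committee definitions of single events do not settle which events enter this endpoint, or what the historical series counted.

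Two stronger readings should be resisted. A reader might infer that serious late bleeding without re-operation is captured only by the Other category. Section 13 also counts fluid or clot in the pericardial space drained by catheter, and in the pleural space drained by chest tube. A reader might also infer that deleting *cerebrovascular* from Section 8 gives one scope. It does not, because Section 2 and Sections 4 and 12 still differ over *and*.

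**Conclusion.** Wrong as written, and minor. Safety (b) names a comparator that counts different events from its numerator, so the SAE part of secondary objective (a) has no like-for-like comparison. Safety (a), Safety (c) and the MACE hypothesis are unaffected.

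A reader might go further and infer that the mismatch is biased against the new operation because the SAE set is broad, or in its favour because Section 8 narrows it. The documents support neither. They give no historical rate or definition, and they do not fix the scope.

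The conclusion assumes that the sentence would be followed literally and that MACE in the historical series resembles the trial's own definition. If a historical series used MACE for some other event set, the comparison would still need its definition stated and matched.

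**What to change.** 1. In Section 12, Safety (b), replace the MACE comparator. Suggested text: *The 12-month rate will be set against the Cox-Maze IV rate for the same event type, under the same definition and 12-month window, with the source and value named.*
2. If no such rate exists, make the SAE part of objective (a) descriptive. Report 12-month thromboembolic and hemorrhagic event rates separately, with exact 95% confidence intervals. Leave the MACE hypothesis and Safety (a) as they are.
3. Use one event scope in Sections 2, 4, 8 and 12. Delete *cerebrovascular* in Section 8, and choose either *protocol-defined serious* or *protocol-defined and serious* throughout.
4. If separate rates are reported, state in which group hemorrhagic stroke and drained pericardial or pleural clot are counted. Section 13 already settles one case: "Hemorrhagic conversion of an ischemic stroke should be classified as ischemic".

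The cost is SAP and protocol wording and, under item 2, one table. No new visits or tests are needed, and the Clinical Events Committee already reviews events. The downside is that the SAE part may lose its comparative claim and that the separate rates will be imprecise. With event counts chosen only as examples, exact two-sided 95% limits in 120 patients are: 0 events, upper limit 3.0%; 3 events, 2.5% (0.5% to 7.1%); 6 events, 5.0% (1.9% to 10.6%). These intervals describe precision, not the size of the mismatch.

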13. SPECIFIC ADVERSE EVENT DEFINITIONS

Bleeding

A bleeding event is defined by any one of the following:

- Transfusion of > 2 units RBC within the first 24 hours following surgery
- Death due to hemorrhage
- Re-operation for hemorrhage or tamponade

NOTE: Hemorrhagic stroke is considered a neurological event and not as a separate bleeding event.

Cardiac Arrhythmias

Any documented arrhythmia that results in clinical compromise (e.g., hemodynamic compromise, oliguria, pre-syncope or syncope) that requires hospitalization or requires a physician visit or occurs during a hospital stay.

Cardiac arrhythmias are classified as:

1. Sustained ventricular arrhythmia requiring defibrillation or cardioversion
2. Sustained supraventricular arrhythmia requiring drug treatment or cardioversion
3. Cardiac conduction abnormalities requiring permanent pacemaker

Pericardial Fluid Collection

Accumulation of fluid or clot in the pericardial space that requires surgical intervention or percutaneous catheter drainage. This event will be subdivided into those with clinical signs of tamponade (e.g. increased central venous pressure and decreased cardiac output) and those without signs of tamponade.

Pleural Effusion

Accumulation of fluid or clot in the pleural space documented by chest radiogram or chest CT that requires evacuation with surgical intervention or chest tube placement.

Atrial Rupture

Disruption in the integrity of the left or right atrial wall, documented by direct inspection or diagnostic testing, that necessitates surgical repair.

Valvular Injury

Injury to a cardiac valve (excluding the mitral valve), as evidenced by new regurgitation or stenosis following the treatment intervention. This definition excludes changes to the mitral valve because it will be surgically repaired at the time of the treatment intervention.

Non-infectious Pericarditis

Signs and symptoms of pericardial inflammation, with or without electrocardiographic evidence, requiring pharmacologic anti-inflammatory therapy. This definition excludes infectious pericarditis (see Major Infection infectious pericarditis definition below).

Superior vena cava Stenosis

A \geq 50% decrease in the diameter of the superior vena cava as documented by echocardiography.

Diaphragmatic Paralysis

Phrenic nerve injury as evidenced by new elevation of a hemi-diaphragm on chest radiogram.

Pneumothorax

Presence of gas in the pleural space, documented by chest radiogram or chest CT, that requires evacuation or prolongs the duration of chest tube drainage.

Hepatic Dysfunction

An increase in any two of the following hepatic laboratory values (total bilirubin, aspartate aminotransferase/AST and alanine aminotransferase/ALT) to a level greater than three times the upper limit of normal for the hospital, (or if hepatic dysfunction is the primary cause of death).

Major Infection

A new clinical infection accompanied by pain, fever, drainage and/or leukocytosis that is treated by anti-microbial agents (non-prophylactic). A positive culture from the infected site or organ should be present unless strong clinical evidence indicates the need for treatment despite negative cultures. The general categories of infection are listed below:

Endocarditis

Signs, symptoms and laboratory findings consistent with endocarditis, including but not limited to fever \geq 38.0o C, positive blood cultures, new regurgitant murmurs or heart failure, evidence of embolic events (e.g., focal neurologic impairment, glomerulonephritis, renal and splenic infarcts, and septic pulmonary infarcts), and peripheral cutaneous or mucocutaneous lesions (e.g., petechiae, conjunctival or splinter hemorrhages, Janeway lesions, Osler's nodes, and Roth spots). Echocardiographic evidence of a new intra-cardiac vegetation with or without other signs and symptoms should be considered adequate evidence to support the diagnosis of endocarditis. TEE should be the modality of choice for diagnosis of prosthetic valve endocarditis.

Mediastinitis/Deep Sternal Wound Infection

Signs and symptoms consistent with mediastinitis, include but are not limited to fever, chills, leukocytosis and chest or back pain, and mediastinal inflammation documented by diagnostic testing (e.g., chest CT). Information regarding deep sternal wound infections will be collected.

Infectious Pericarditis

Signs and symptoms, including but not limited to fever, leukocytosis and pericardial inflammation, necessitating surgical exploration, drainage and treatment with intravenous antibiotics.

Sepsis

Evidence of systemic involvement by infection, manifested by positive blood cultures and/or hypotension. In addition, we will record systemic antibiotic use for presumptive sepsis.

Localized Infection

Infection localized to any organ system or region other than the mediastinum, pericardium, or endocardium without evidence of systemic involvement (see sepsis definition), ascertained by standard clinical methods and either associated with evidence of bacterial, viral, fungal or protozoal infection, and/or requiring empirical treatment.

Heart Failure

New onset of signs or symptoms of congestive heart failure or worsening of preexisting heart failure by ≥ 1 NYHA class.

Myocardial Infarction

Myocardial infarction (MI) should be classified when there is evidence of myocardial necrosis in a clinical setting consistent with myocardial ischemia.

Under these conditions, any one of the following criteria meets the diagnosis for myocardial infarction⁴:

Myocardial Infarction

Detection of rise and/or fall of cardiac biomarkers (preferably troponin) with at least one value above the 99th percentile of the upper reference limit (URL) together with evidence of myocardial ischemia with at least one of the following:

- Symptoms of ischemia;

- ECG changes indicative of new ischemia (new ST-T changes or new left bundle branch block [LBBB]);
- Development of pathological Q waves in the ECG;
- Imaging evidence of new loss of viable myocardium or new regional wall motion abnormality.

Peri-CABG Myocardial Infarction

For CABG in patients with normal baseline troponin values, elevations of cardiac biomarkers above the 99th percentile URL are indicative of peri-procedural myocardial necrosis. By convention, increases in biomarkers $> 5 \times$ 99th percentile URL plus either new pathological Q waves or new LBBB, or angiographically documented new graft of native coronary artery occlusion, or imaging evidence of new loss of viable myocardium have been designated as defining CABG-related MI.

Peri-Percutaneous Intervention (PCI) Myocardial Infarction

For PCI in patients with normal baseline troponin values, elevations of cardiac biomarkers above the 99th percentile URL are indicative of peri-procedural myocardial necrosis. By convention, increases in biomarkers $> 3 \times$ 99th percentile URL have been designated as defining PCI-related MI. A subtype related to a documented stent thrombosis is recognized.

Sudden unexpected cardiac death, involving cardiac arrest, often with symptoms suggestive of myocardial ischemia, and accompanied by presumed new ST elevation or new LBBB, and/or evidence of fresh thrombus by coronary angiography and/or autopsy, with death occurring before blood samples obtained, or at a time before the expected appearance of cardiac biomarkers in blood will be classified as a mortality due to MI.

Neurologic Dysfunction

Any new, temporary or permanent, focal or global neurological deficit ascertained by a standard neurological examination (administered by a neurologist or other qualified physician and documented with appropriate diagnostic tests and consultation note). The examining physician will distinguish between a transient ischemic attack (TIA), which is fully reversible within 24 hours (and without evidence of infarction), and a stroke, which lasts longer than 24 hours (or less than 24 hours if there is evidence of infarction). The Modified Rankin Scale and the NIH Stroke Scale (NIHSS) must be administered at time of event (within 72 hours following the event) and 90 days following the event

to document the presence and severity of neurological deficits. The Modified Rankin Scale and NIHSS can be found in Appendix III.

Each neurological event must be subcategorized as: Transient Ischemic Attack

Defined as an acute event that resolves completely within 24 hours with no imaging evidence of infarction.

Ischemic or Hemorrhagic Stroke (Cerebrovascular Accident)

Defined as an event that persists beyond 24 hours or less than 24 hours associated with infarction on an imaging study. Hemorrhagic conversion of an ischemic stroke should be classified as ischemic.

Toxic Metabolic Encephalopathy

Defined as a disorder of the brain function that arises from abnormal systemic metabolism or exogenous substances, altering awareness and/or consciousness, in which there is a non-focal neurological examination and a negative brain image.

Other Neurologic Dysfunction

Renal Events

Two categories of renal events will be identified:

- Renal Dysfunction: Abnormal kidney function defined by $> 100\%$ rise in serum creatinine (Cr) from baseline, and $Cr > 2.0$
- Renal Failure: New requirement for hemodialysis related to renal dysfunction. This definition excludes aquapheresis for volume removal alone.

Respiratory Failure

Impairment of respiratory function requiring re-intubation, tracheostomy or the inability to discontinue ventilatory support within 48 hours post-surgical intervention. This excludes intubation for re-operation or temporary intubation for diagnostic or therapeutic procedures.

Right Heart Failure

Symptoms and signs of persistent right ventricular dysfunction [central venous pressure (CVP) > 18 mmHg with a cardiac index < 2.0 L/min/m² in the absence of elevated left atrial/pulmonary capillary wedge pressure (> 18 mmHg), tamponade, ventricular arrhythmias or pneumothorax] requiring RVAD implantation, inhaled nitric oxide or inotropic therapy, for a duration of > 7 days.

Arterial Non-CNS Thromboembolism

An acute systemic arterial perfusion deficit in any non-cerebrovascular organ system due to thromboembolism confirmed by one or more of the following:

- Standard clinical and laboratory testing
- Operative findings
- Autopsy findings

This definition excludes neurological events.

Venous Thromboembolic Event

Evidence of venous thromboembolic event (e.g. deep vein thrombosis, pulmonary embolism) by standard clinical and laboratory testing.

Wound Dehiscence

Disruption of the apposed surfaces of a surgical incision, excluding infectious etiology, and requiring surgical repair.

Other

An event that causes clinically relevant changes in the patient's health, or any event that is life-threatening, results in a fatality, results in permanent disability, requires hospitalization, or prolongs an existing hospital stay.

References

